### 2.3.3      *Preclinical Experience*

Detailed information concerning the preclinical studies conducted with ANGPTL3 ASOs can be found in the Investigator's Brochure. A summary is included below.

#### 2.3.3.1      *Preclinical Pharmacology*

The pharmacology of ANGPTL3 ASOs has been examined in multiple *in vitro* cell lines where specific and dose-dependent reduction of ANGPTL3 mRNA and protein was clearly demonstrated, resulting in reductions in apoB secreted protein. The pharmacology of ISIS 563580, an unconjugated 2'-MOE modified ASO that has the same base sequence as AKCEA-ANGPTL3-LRX, at doses higher than planned for AKCEA-ANGPTL3-LRX.

ISIS 563580 has been explored in human ANGPTL3 transgenic mice, wherein liver mRNA and plasma ANGPTL3 protein levels were reduced upon treatment with ISIS 563580.

Reductions in murine ANGPTL3 mRNA and protein were routinely observed in all mouse models treated with a murine-specific ANGPTL3 ASO. Pharmacology studies were done with *Ldlr*-/- mice fed a hypercholesterolemic diet known to develop elevated LDL-C, TG, and atherosclerosis, as well as features of metabolic syndrome (hyperglycemia and hyperinsulinemia) (Huszar et al. 2000; Schreyer et al. 2002; Tsuchiya et al. 2012). Treatment of mice with a murine-specific ANGPTL3 ASO resulted in improvement in all of the aforementioned lipid and metabolic endpoints compared to controls. In all mouse models tested, total plasma cholesterol, LDL-C, TG, and non-esterified fatty acids (NEFA) have been shown to be consistently reduced upon treatment with ANGPTL3 ASOs, while HDL-C is modestly decreased in wild type mice (- 22%), and either stable or increased in others. While a clear mechanistic understanding of HDL-C reductions has not been elucidated, results from *in vitro* reverse cholesterol transport assays suggest that HDL function is maintained.

Administration of AKCEA-ANGPTL3-LRX, a human specific ANGPTL3 ASO, to human *ANGPTL3* transgenic mice led to significant, dose-dependent reductions in hepatic ANGPTL3 mRNA. In diet challenged mice, administration of ISIS 731875, a mouse-specific and GalNAc-modified ASO targeting ANGPTL3, led to dose-dependent reductions in both hepatic ANGPTL3 mRNA and plasma ANGPTL3

with concomitant reductions in plasma TG and cholesterol. Importantly, the potency and the lipid-lowering effects of the ANGPTL3 ASO were independent of diet.

Finally, administration of a mouse-specific ANGPTL3 ASO to western diet fed *Ldlr*-/-, a mouse model of FH, also led to significant reductions in hepatic ANGPTL3 mRNA and plasma ANGPTL3 protein with concomitant reductions in plasma TG and LDL-C that were similar to what was observed in wild type western diet fed mice, indicating that the absence of *Ldlr* does not affect the ASOs potency or lipid-lowering effects. This suggests that administration of ANGPTL3 ASO administration is a promising target for clinical study in familial hypercholesterolemia patients.

While formal pharmacology studies have not been conducted in the monkey with the human ANGPTL3 ASO, hepatic mRNA expression has been shown to be reduced by more than 60% in cynomolgus monkeys, the same model used to conduct the toxicology evaluation.

### 2.3.3.2 Preclinical Toxicology

General toxicology studies for AKCEA-ANGPTL3-LRX consisted of sub-chronic (16-week) and chronic (26- or 39-week) toxicity studies CD-1 in mice and cynomolgus monkeys. Since AKCEA-ANGPTL3-LRX is not fully complementary to the mouse ANGPTL3 transcript, treatment group receiving a mouse-specific inhibitor (ISIS 731875) was also included in the mouse study. Please refer to the Investigator Brochure for a detailed description of the preclinical toxicology and pharmacokinetics with AKCEA-ANGPTL3-LRX.

Pharmacokinetic data confirmed continuous and dose-dependent exposure to AKCEA-ANGPTL3-LRX. An estimated liver and plasma elimination half-life values of approximately 1 week and 3-4 weeks for 2 mg/kg and 35 mg/kg, respectively, were observed in monkeys. The most noteworthy findings observed in mice and monkeys following AKCEA-ANGPTL3-LRX treatment were, in general, non-specific class effects related to the uptake and accumulation of ASO and no toxicologically relevant findings were considered related to the pharmacologic inhibition of hepatic ANGPTL3 expression, either with the present series of studies or with the former development candidate targeting ANGPTL3. There were no test-article related changes in PLT count in either mouse or monkey in both sub-chronic and chronic studies.

The most noteworthy finding in the monkey was the kidney alteration (hypoalbuminemia and proteinuria) seen in one early-sacrifice animal from the 16-week study at 35 mg/kg/week, a dose equivalent to at least ~190-fold of the 40 mg weekly clinical doses by plasma AUC. Non-dose dependent increases in renal protein excretion (up to 2.2-fold in quantitative urine protein, protein/creatinine ratio or urine albumin) were also observed at 8 and/or 35 mg/kg/week (> ~ 30 to 190-fold of the 40 mg weekly clinical doses by plasma AUC) at the 16-week scheduled terminal necropsy. However, Similar kidney alterations were not seen at the 6-week interim at any doses or in the 39-week chronic monkey study up to 12 mg/kg/week (> ~200-fold of the 20 mg weekly clinical dose by plasma AUC).

Additional findings related to ASO liver accumulation included increased alanine aminotransferase (ALT), aspartate aminotransferase (AST), and alkaline phosphatase (ALP) at  $\geq$  8 mg/kg/week in the 16- and 26-week mouse studies, and were correlated with individual hepatocyte necrosis (minimal to mild) in mouse liver. Those changes were most prominent in the high dose groups (50 and 24 mg/kg/week for the 16- and 26-week studies, respectively). Conversely, no changes in liver enzymes were observed in monkeys from the 39-week toxicity study up to 12 mg/kg/week. In the 16-week monkeys study, increase in ALT was only evident in one early-sacrifice animal at 35 mg/kg/week, and non-statistically significant

increases in ALT (<2-fold of the pre-study baseline) were also observed in the interim- and terminal-sacrifice animals at  $\geq 8$  mg/kg/week but showed no microscopic correlates or dose-dependency.

Given the spectrum and severity of the test article-related clinicopathologic alterations present in monkeys at doses  $\leq 12$  mg/kg/week ( $> \sim 100$ -fold of the 40 mg weekly clinical dose by plasma AUC) during the 39-week treatment phase, none would be regarded to represent an adverse effect (Dorato and Engelhardt 2005; Everds et al. 2013). Considering the monkey to be the most relevant species, these data have characterized the safety profile and established appropriate therapeutic margins for the clinical evaluation of AKCEA-ANGPTL3-LRX in humans.

### 2.3.4 Clinical Experience

Detailed information concerning the clinical studies conducted with AKCEA-ANGPTL3-LRX can be found in the Investigator's Brochure. A summary is included below.

The study drug, AKCEA-ANGPTL3-LRX, is being evaluated in Phase 1 in the clinical setting with single doses up to 120 mg and multiple doses up to 60 mg (once per week for 6 weeks). The parent drug ISIS 563580, an unconjugated 2'-MOE modified ASO that has the same base sequence as AKCEA-ANGPTL3-LRX, was also evaluated in a blinded, placebo-controlled Phase 1 study.

AKCEA-ANGPTL3-LRX Phase 1 SAD/MAD interim analysis of Study ISIS 703802-CS1 was performed in 44 subjects administered single ascending (20, 40 and 80 mg) or multiple ascending doses (10, 20, 40 and 60 mg/week for 6 weeks). Twelve participants were randomly assigned to single-dose groups (9 to active-agent dose groups and 3 to the placebo group) and 32 were randomly assigned to multiple-dose groups (24 to active-agent dose groups and 8 to the placebo group). The main endpoints of the study were safety, tolerability, pharmacokinetics, pharmacodynamics and changes in lipids and lipoproteins. After 6 weeks of treatment, persons in the multiple dose groups treated with AKCEA-ANGPTL3-LRX had dose-dependent reductions in levels of ANGPTL3 protein (reductions of 46.6 to 84.5% from baseline,  $P < 0.01$  for all doses vs. placebo 1.6%) and in levels of triglycerides (reductions of 33.2 to 63.1% vs placebo 11.4%), LDL cholesterol (1.3 to 32.9% vs placebo 13.6%), very-low-density lipoprotein cholesterol (27.9 to 60.0% vs placebo 4.0%), non-high-density lipoprotein cholesterol (10.0 to 36.6% vs placebo 9.1%), apolipoprotein B (3.4 to 25.7% vs placebo 11.0%), and apolipoprotein C-III (18.9 to 58.8% vs placebo 3.1%). There were no serious adverse events documented during the trial. No protocol-defined injection-site reactions were reported. Of those participants who received the multiple-dose regimen, three reported headache (one who received placebo and two who received ANGPTL3-LRX) and three reported dizziness (two who received placebo and one who received ANGPTL3-LRX). There was no clinical evidence of prothrombotic effects, bleeding episodes, significant decreases in platelet count or thrombocytopenia, or significant changes in liver or renal function. One subject in the 20 mg MAD group was lost to follow-up after 5 doses. There were no other discontinuations during the treatment period (Graham et al. 2017).

The pharmacokinetics of AKCEA-ANGPTL3-LRX evaluated in Study ISIS 703802-CS1 showed rapid absorption following SC administration, with median time to maximum plasma concentrations ( $T_{max}$ ) ranging from 1 to 6 hours. Similar  $T_{max}$  values were observed at all dose levels. After reaching  $C_{max}$ , plasma concentrations of AKCEA-ANGPTL3-LRX declined in a multi-phasic fashion with a rapid disposition phase, followed by a slower elimination phase with terminal elimination half-life of 3 to 5 weeks. The peak ( $C_{max}$ ) and total exposure (AUC) after a single SC dose increased approximately dose proportionally from 20 to 40 mg, and greater than dose proportionally from 40 to 80 mg, suggesting more efficient tissue uptake at lower doses. After single and multiple SC doses in the range of 10 to 60 mg, the

$C_{max}$  and AUC increased approximately dose proportionally. No accumulation based on  $C_{max}$  or AUC was observed after 6 weekly doses.

#### **2.3.4.1 ISIS 563580-CS1 Phase 1 SAD/MAD**

In a Phase 1 study, ISIS 563580-CS1, healthy volunteers received subcutaneous administration of ISIS 563580 from 50 to 400 mg as a single dose, or 100 to 400 mg as multiple doses (8 doses in 36 days). Overall, the safety findings from this study suggest that ISIS 563580 was not associated with any safety concerns. There were 383 adverse events (AE) reported in the ISIS 563580-treated subjects of which 363 (95%) were mild in severity. For the multiple-dose subjects, the most common treatment-emergent adverse events were AEs at the injection site. There was 1 serious adverse event (SAE) in the study of periorbital cellulitis which was considered a medically important event by the Investigator and was also considered unlikely related to Study Drug by the Investigator. Together, the above suggest that ISIS 563580 was well-tolerated at the doses and regimen given, which exceed the dose levels and cumulative exposures to be tested in the current study. There were no clinically-relevant changes in laboratory assessments and the heparin dose of 80 U/kg was well-tolerated in support of the post-heparin procedures. ISIS 563580 produced dose-dependent reductions in plasma ANGPTL3 (up to 93%; group means up to 84%), TG (up to 63%; group means up to 49%) and TC (up to 46%; group means up to 28%) at Day 36 (Brandt et al. 2015).

### **2.4 Rationale for Dose and Schedule of Administration**

Safety data from the available chronic mouse (26-week) and monkey (39-week) studies support once-weekly dosing for chronic administration. The No Adverse Effect Level (NOAEL) for AKCEA-ANGPTL3-LRX in chronic monkey study was determined to be 12 mg/kg/wk.

Preclinical pharmacology experiments in Tg-mice and in non-human primates demonstrated that AKCEA-ANGPTL3-LRX achieved an equivalent reduction in ANGPTL3 plasma concentration to that of the unconjugated form, at 1/10th of the unconjugated ASO (ISIS 563580) dose. The dose level planned for this study for AKCEA-ANGPTL3-LRX is 20 mg, which is the lowest dose that provided maximum TG lowering of approximately 60% in Study ISIS 703802-CS1 and is approximately 200-fold lower than NOAEL dose in monkey at 12 mg/kg/wk in the 39-week chronic monkey study up to terminal necropsy.

An interim analysis of the phase 1 study completed for all but the 120 mg single dose cohort showed approximately 60% reduction of TG at 20 mg dose. However, at 40 mg and 60 mg dose the TG reduction did not differ significantly from 20 mg dose. Thus, the lower dose was selected for this study for optimal risk to benefit.

### **2.5 Benefit-Risk Assessment**

#### **2.5.1 Benefit Assessment**

The current study is designed to evaluate the safety and tolerance of AKCEA-ANGPTL3-LRX in FCS subjects. The dose selected is expected to reduce ANGPTL3 and result in a reduction of the severe hypertriglyceridemia and chylomicronemia that afflicts FCS subjects. Importantly, although we do not know if subjects participating in this study would necessarily benefit from the treatment, the increased understanding of AKCEA-ANGPTL3-LRX in this population is expected to result in improved treatment options that would ultimately benefit all FCS patients, including participants in the study. Due to the short duration of this trial any benefit observed is not expected to persist beyond the end of the study.

### 2.5.2 Risk Assessment

The known potential risks to study participants associated with AKCEA-ANGPTL3-LRX are elaborated on in the Guidance to Investigator section of the Investigator's Brochure.

- In preclinical mouse studies, there were increases in ALT and AST and were correlated with increased incidence and/or severity of necrosis of individual hepatocytes (minimal to mild in severity). Those changes were most prominent in the high dose groups and showed no clear progression over time. No increases in liver enzymes were observed in monkeys from the 39-week toxicity study up to 12 mg/kg/week (~200-fold of the 20 mg clinical dose by plasma AUC). In the 16-week monkey study, increase in ALT was only evident in 1 early-sacrifice animal at 35 mg/kg/week, no meaningful increase in ALT was observed in the schedule sacrificed animals.
- There were no observed significant changes in ALT and liver function in an ongoing Phase 1 human study ([Graham et al. 2017](#)). The risk of observing significant ALT/AST changes in this clinical human study is expected to be relatively low with the proposed 20 mg dose. However, to evaluate and mitigate the potential for liver enzyme abnormalities, regular liver chemistry monitoring and stopping rules are included in the study as specified in [Sections 8.5](#) and [8.6](#).
- Injection site adverse events, while not considered safety issues, may affect the ability of the patient to tolerate dosing. Injection site adverse events are the most common side effects observed following SC administration of 2 $\delta$ -MOE ASOs and are dose and concentration dependent. Erythema is the most prevalent characteristic. Generally, these events are mild and reversible, resolve spontaneously and do not worsen with time. The histologic findings are consistent with a local inflammatory response. While planned doses of AKCEA-ANGPTL3-LRX for clinical evaluation are generally below the doses that are historically associated with these effects, patients should be informed of the possibility of occurrence of injection site adverse events. Symptomatic interventions such as icing of the injection site or administration of NSAIDs prior to and/or after the SC dosing have been utilized.

While the long term consequences of reducing ANGPTL3 as a target with the study drug are not known at this time, there is evidence in literature in humans in whom ANGPTL3 is absent from plasma, due to homozygous or compound heterozygous ANGPTL3 mutations, present a pan-hypobetalipoproteinemia phenotype, with generalized and marked decreases (~50% to 70%) in all apoB-100 containing lipoproteins, including VLDL and LDL, as well as HDL. This clinical phenotype has been termed familial combined hypolipidemia or FHBL2 ([Romeo et al. 2009](#); [Musunuru et al. 2010](#); [Martin-Campos et al. 2012](#); [Minicocci et al. 2012](#); [Noto et al. 2012](#); [Pisciotta et al. 2012](#); [Wang et al. 2015](#)). Clinical studies in FHBL2 suggest a trend toward lower glucose and insulin levels and despite a reported decrease in VLDL production, there is no apparent difference in hepatic fat content compared to controls. Remarkably, diabetes and cardiovascular disease are reportedly absent from those with homozygous FHBL2 and no adverse clinical phenotype has been reported to date.

### 2.5.3 Overall Assessment of Benefit:Risk

Fasting plasma triglyceride (TG) levels in FCS patients are typically 10-fold to 100-fold above normal (1,500 to 15,000 mg/dL), despite extreme dietary fat restriction (20 g or approximately 15-20% of daily calorie intake) ([Brunzell 1999-2011](#)). Given the unmet medical need for FCS patients, AKCEA-ANGPTL3-LRX has demonstrated the ability to reduce TGs by 60% in the Phase 1/2 study in healthy volunteers. The objective of this study is to assess the effect of TG lowering in FCS patients. Although the FCS patients enrolled in this study will not derive long term benefits due to the short duration of the

study, the information obtained in the course of this study is critical to further development of AKCEA-ANGPTL3-LRX for this disease with an extremely high unmet need. Taking into account the measures taken to minimize risk to subjects participating in this study, the fact that potential risks identified in association with AKCEA-ANGPTL3-LRX are minimal and are manageable by routine monitoring exposure of FCS patients in this study is justified by the anticipated benefits that may be afforded to the wider population of FCS subjects by continued development of AKCEA-ANGPTL3-LRX.

### **3. EXPERIMENTAL PLAN**

#### **3.1 Study Design**

This will be a Phase 2 open-label multiple-dose study of approximately 3 subjects with FCS and will be treated with AKCEA-ANGPTL3-LRX.

Subject will receive 20 mg of AKCEA-ANGPTL3-LRX SC weekly.

#### **3.2 Number of Study Centers**

This study will be conducted at a single center but could be expanded to more than one center.

#### **3.3 Number of Subjects**

Approximately 3 subjects will be treated in this study.

#### **3.4 Overall Study Duration and Follow-up**

The study will consist of a screen/ run-in period, study treatment, post-treatment and long term follow-up. Please refer to the Schedule of Procedures in [Appendix A](#).

Subjects may be required to attend additional visits for monitoring of adverse events or abnormal investigation results. The frequency of additional monitoring will be determined by the Study Medical Monitor in consultation with the Investigator.

The length of subjects' participation in the study may be up to 34 weeks, including an up to 8-week screening period, that includes a 6-week diet stabilization / run-in period, a 13-week treatment period, and a 13-week post-treatment evaluation period. Subjects will perform the first dosing at the site, with subsequent dosing occurring at home following training on how to dose. The diet stabilization period may be reduced if the patient is following a stable low fat diet for optimal disease control and disease management prior to screening.

##### **3.4.1 Screening**

Subject eligibility for the study will be determined within 56 days/8 weeks prior to study entry.

##### **3.4.2 Treatment**

Eligible subjects will receive the first dose of study drug at the Study Center, at which time they will also be trained on self-administration of Study drug. Subsequent administrations of study drug may occur at home or in the study center. Eligible subjects will report to the Study Center for assessments at specified intervals throughout the 13-week treatment period as detailed in the Schedule of Procedures in [Appendix A](#).

**3.4.3 Post-Treatment**

Subjects are to return to the Study Center for follow-up visits every four weeks (refer to the Schedule of Procedures in [Appendix A](#)). The final study visit will be Study Week 26.

**3.5 End-of-Study**

The End-of-Study is defined as the last subject's last visit.

**4. SUBJECT ENROLLMENT****4.1 Screening**

Before subjects may be enrolled into the Study, the Sponsor or designee requires a copy of the Study Center's written independent ethics committee/institutional review board (IEC/IRB) approval of the protocol, informed consent form, and all other subject information and/or recruitment material.

Subjects must sign the informed consent form before any screening tests or assessments are performed. At the time of consent, the subject will be considered enrolled into the Study and will be assigned a unique screening number before any Study procedures, including screening procedures, are performed. At the time of randomization or registration, subjects will be assigned a unique subject identification number. This number will be used to identify the subject throughout the trial and must be used on all study documentation related to that subject. The screening number and subject identification number must remain constant throughout the entire trial. Screening numbers and subject identification numbers, once assigned, will not be reused.

**4.2 Registration**

Patients will be registered after all screening assessments have been completed and after the Investigator has verified that they are eligible per criteria in [Sections 5.1](#) and [5.2](#). No subject may begin treatment prior to assignment of a unique subject identification number.

**4.3 Replacement of Subjects**

Due to the small number of subjects participating in the study, subjects who withdraw from the study may be replaced by allowing a new subject to be screened and enrolled. The subjects who withdrew for safety reasons will not be replaced.

**5. SUBJECT ELIGIBILITY**

To be eligible to participate in this study candidates must meet the following eligibility criteria within 56 days of treatment day 1 or at the time point specified in the individual eligibility criterion listed.

**5.1 Inclusion Criteria**

1. Must have given written informed consent (signed and dated) and any authorizations required by local law and be able to comply with all study requirements.
2. Males or females aged  $\geq 18$  years old at the time of informed consent.
3. Genetically confirmed homozygote or compound heterozygote for known null loss-of-function mutations in the LPL gene.
4. Fasting TG  $\geq 750$  mg/dL (8.4 mmol/L) at Screening. If the fasting TG  $< 750$  mg/dL up to 2 additional tests may be performed in order to qualify.

5. Willing to follow a diet comprising  $\leq 20\text{g}$  fat per day during the study.
6. Females: must be non-pregnant and non-lactating and either:
  - i. Surgically sterile (e.g., tubal occlusion, hysterectomy, bilateral salpingectomy, bilateral oophorectomy);
  - ii. Post-menopausal (defined as 12 months of spontaneous amenorrhea in females  $> 55$  years of age or, in females  $\leq 55$  years, 12 months of spontaneous amenorrhea without an alternative medical cause and FSH levels in the postmenopausal range for the laboratory involved);
  - iii. Abstinent\* or,
  - iv. If engaged in sexual relations of child-bearing potential, agree to use 2 highly effective contraceptive methods (refer to [Section 6.3.1](#)) from the time of signing the informed consent form until at least 13 weeks after the last dose of Study Drug (AKCEA-ANGPTL3-LRX).
7. Males: Surgically sterile or if engaged in sexual relations with a female of child-bearing potential, subject is utilizing an acceptable contraceptive method (refer to [Section 6.3.1](#)) from the time of signing the informed consent form until at least 13 weeks after the last dose of Study Drug (AKCEA-ANGPTL3-LRX).

\* Abstinence is only acceptable as true abstinence, i.e., when this is in line with the preferred and usual lifestyle of the patient. Periodic abstinence (e.g., calendar, ovulation, symptothermal, post-ovulation methods), declaration of abstinence for the duration of a trial and withdrawal are not acceptable methods of contraception.

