Study Population	
Inclusion:
 
 
1. Must have given written informed consent (signed and dated) and any authorizations required by local law and be able to comply with all study requirements.
 
2. Males or females aged <math>\geq</math> 18 years old at the time of informed consent
 
3. Genetically confirmed homozygote or compound heterozygote for known null loss-of-function mutations in the LPL gene.
 
4. Fasting TG <math>\geq</math> 750 mg/dL (8.4 mmol/L) at Screening. If the fasting TG <math><</math> 750 mg/dL up to 2 additional tests may be performed in order to qualify.
 
5. Willing to follow a diet comprising <math>\leq</math> 20g fat per day during the study
 
6. Females: must be non-pregnant and non-lactating and either; 
 
i. Surgically sterile (e.g., tubal occlusion, hysterectomy, bilateral salpingectomy, bilateral oophorectomy);
 
ii. Post-menopausal (defined as 12 months of spontaneous amenorrhea in females <math>></math> 55 years of age or, in females <math>\leq</math> 55 years, 12 months of spontaneous amenorrhea without an alternative medical cause and FSH levels in the postmenopausal range for the laboratory involved);
 
iii. Abstinent* or,
 
iv. If engaged in sexual relations of child-bearing potential, agree to
 
 
 

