## 2. BACKGROUND AND RATIONALE

### 2.1 Overview of Disease

Familial Chylomicronemia Syndrome (FCS) is an inherited disease characterized by severe hypertriglyceridemia and chylomicronemia. It is a rare autosomal recessive disease that can be diagnosed either in childhood or adulthood.

FCS is characterized by frequent and severe abdominal pain, repetitive colicky pain, repeated episodes of potentially fatal acute pancreatitis, and in children, can result in a failure to thrive (Brunzell 1999-2011; Tremblay et al. 2011). Physical examination frequently reveals eruptive xanthomas, lipemia retinalis and hepatosplenomegaly, and plasma from patients appears lactescent, interfering with determination of other laboratory parameters (Tremblay et al. 2011). Fasting plasma triglyceride (TG) levels in FCS patients are typically 10-fold to 100-fold above normal (1,500 to 15,000 mg/dL), despite extreme dietary fat restriction (20 g or approximately 15-20% of daily calorie intake) (Brunzell 1999-2011).

Patients with FCS often present in infancy or childhood with recurrent episodes of abdominal pain or pancreatitis, eruptive xanthomas or hepatomegaly. The diagnosis of FCS is then established by genotyping or confirmation of very low or absent lipoprotein lipase (LPL) enzyme activity in post heparin plasma (Brunzell 1999-2011).

Patients with FCS carry a heavy burden of medical complications, the most serious being an extreme risk of recurrent and potentially fatal pancreatitis. Due to the recurrent episodes of acute pancreatitis, these patients may also develop chronic pancreatitis and signs of exocrine or endocrine pancreatic insufficiency, including diabetes mellitus (Gaudet et al. 2013). While the pathophysiology underlying chylomicron-related pancreatitis has not been completely elucidated, one hypothesis is that large chylomicrons lodged in pancreatic capillaries are exposed to pancreatic lipase, with the subsequent release of free fatty acids through the hydrolysis of chylomicron-associated TGs. High concentrations of free fatty acids are thought to damage pancreatic cells leading to emergent pancreatitis (Yang et al. 2009; Berglund et al. 2012).

The etiology of extreme hypertriglyceridemia in FCS is considered to be ineffective triglyceride clearance, due to an extremely low level of LPL activity. LPL normally functions to hydrolyze

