## **10. STATISTICAL CONSIDERATIONS**

### **10.1 Study Endpoints, Subsets, and Covariates**

For fasting lipid measurements, the values for the Month 3 analysis time point are defined as the average of Week 13 (Day 85) and Week 14 (Day 92) fasting assessments.

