**10.4 Definition of Baseline**

Definitions of baseline are given below for the purposes of the final analysis.

For fasting lipid measurements, the baseline is defined as the average of Day 1 pre-dose assessment and the last measurement prior to Day 1.

For other measurements, baseline will be the last non-missing assessment prior to the first dose of Study Drug.

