### ***10.6.3 Efficacy Analysis***

Percent change and change from baseline to Month 3 in fasting TG will be summarized. Response rate of patients with fasting serum TG < 750 mg/dL or achieving fasting TG  $\geq$  40% reduction from baseline at Month 3 will be summarized. Response analysis will also be conducted using a range of fasting serum TG thresholds for determination of responder status.

Percent change and change from baseline to Month 3 will also be summarized by treatment group for other fasting lipid measures including ANGPTL3, non-HDL-C, apoB, HDL-C, apoA-1, VLDL-C, and LDL-C, total cholesterol, and fasting total apoC-III.

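### Inclusion criterion 4 equates 750 mg/dL with 8.4 mmol/L, but 750 mg/dL of triglyceride is 8.47 mmol/L; the slip touches eligibility only, in a band of about 6 mg/dL

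*Combined protocol and SAP*

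**What the plan says.** Section 5.1, criterion 4, requires a fasting TG of at least 750 "mg/dL (8.4 mmol/L) at Screening". The synopsis repeats the pair: "750 mg/dL (8.4 mmol/L) at Screening". Both places read the same in the July 2017 protocol and in Amendment 1.

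The second sentence of the criterion deals with a patient who falls short. It names the limit in one unit only: a patient below 750 "mg/dL up to 2 additional tests may be performed in order to qualify".

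The same number returns as a response limit. Section 10.6.3 plans a "Response rate of patients with fasting serum TG < 750 mg/dL or achieving fasting TG" at least a 40% reduction from baseline at Month 3. No mmol/L value appears there.

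No section gives a conversion factor, names the unit in which the laboratory will report TG, or says which unit governs if the two figures in criterion 4 disagree.

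**The concern.** An eligibility limit is applied as printed. When it is given in two units, the two figures should pick out the same patients. Here the mmol/L figure looks too low for its mg/dL partner, so the unit on the laboratory report could decide whether a patient just under 750 mg/dL enters. The criterion would also disagree with itself: the first sentence, read in mmol/L, would accept a result that the second sentence, read in mg/dL, sends for retest.

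What is at stake is consistent application of one entry criterion. Because 750 mg/dL also serves as a response limit, it is worth checking how far the slip reaches.

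**Working it through.** **Inputs**
- Entry limit: 750 mg/dL and 8.4 mmol/L (Section 5.1, criterion 4; synopsis).
- Retest trigger: below 750 mg/dL (Section 5.1, criterion 4).
- Response limit: below 750 mg/dL (Section 10.6.3).
- Typical fasting TG in familial chylomicronemia syndrome (FCS): "1,500 to 15,000 mg/dL), despite extreme dietary fat restriction" (Section 2.1).
- Conversion factor f, in mg/dL per mmol/L: not in the documents. Assumed 88.57, the conventional value for triglyceride, with a range of 88.5 to 88.6.

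**Step 1: can the printed 8.4 be reproduced?** mmol/L = (mg/dL) / f.
- f = 88.57: 750 / 88.57 = 8.468.
- f = 88.5: 750 / 88.5 = 8.475.
- f = 88.6: 750 / 88.6 = 8.465.

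To two decimals, at the central factor, the equivalent is 8.47. To one decimal it is 8.5 across the whole range. The printed 8.4 is not reproduced.

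**Step 2: what would give 8.4?** Rounding to 8.4 requires a result between 8.35 and 8.45, so f must lie between 750 / 8.45 = 88.76 and 750 / 8.35 = 89.82. That is outside the conventional range. A coarse multiplier does it (750 × 0.0112 = 8.40, implying f = 750 / 8.4 = 89.29), as does cutting 8.47 off after one decimal. The documents do not show which was used.

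**Step 3: size of the gap.** mg/dL = (mmol/L) × f.
- 8.4 × 88.57 = 744.0 (743.4 at f = 88.5; 744.2 at f = 88.6).
- Gap: 750 − 744 = 6 mg/dL, and 6 / 750 = 0.8%.

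**Step 4: which results are affected?** To two decimals, these are 8.40 to 8.46 mmol/L.
- 8.40 × 88.57 = 744.0 mg/dL.
- 8.43 × 88.57 = 746.6 mg/dL.
- 8.46 × 88.57 = 749.3 mg/dL.

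All three meet the printed mmol/L limit. All three fall below 750 mg/dL, and so call for a retest under the second sentence.

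**Step 5: does the correction close the gap?** 8.47 × 88.57 = 750.2 mg/dL (749.6 at f = 88.5; 750.4 at f = 88.6), which is within half a mg/dL of 750 over the assumed range. One decimal is looser: 8.5 × 88.57 = 752.8 mg/dL, about 3 mg/dL on the strict side.

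**The case against.** The strongest reply is that the criterion leads with mg/dL, puts mmol/L in parentheses, and words its retest rule in mg/dL alone. On that reading 750 mg/dL governs, a result of 744 to 749 mg/dL simply fails that test, and 8.4 is an editorial slip. The disease description in Section 2.1 and the response limit in Section 10.6.3 are in mg/dL too. Typical FCS levels start at about twice the entry limit, and about 3 subjects are planned. All of this bears on how often the slip could bite, and it stands. It does not make the printed figure right, and nothing tells a site reading mmol/L reports to ignore it.

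A reader might infer more: that 8.40 to 8.46 mmol/L both qualifies a patient and counts as a Month 3 response, giving a response without change, and that one such patient among three would shift the response rate by 33 points. The documents do not support this.
- Such a value qualifies only if the site applies the parenthetical figure, and the reporting unit is not stated.
- Section 10.6.3 contains no mmol/L value, so 8.4 cannot misclassify a response. A Month 3 value of 746 mg/dL is below 750 and is classified as written.
- The values compared are not single screening results. Month 3 is the "average of Week 13 (Day 85) and Week 14 (Day 92) fasting assessments" (Section 10.1), and for lipids "the baseline is defined as the average of Day 1 pre-dose assessment and the last measurement prior to Day 1" (Section 10.4).
- A responder with almost no change, for example 751 mg/dL at entry and 749 at Month 3, arises because 750 mg/dL is both entry and response limit. Correcting the conversion would leave that possible.
- The 33 points are just 1 divided by 3 and do not measure this error.

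**Conclusion.** The two limits in criterion 4 are not equal. Given the assumed factor of 88.5 to 88.6 mg/dL per mmol/L, 750 mg/dL is 8.47 mmol/L and 8.4 mmol/L is about 744 mg/dL, and ordinary rounding does not explain the difference. A site working in mmol/L could admit, on a single test, a patient whom the same criterion in mg/dL would send for retest.

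The consequence is small. It is confined to eligibility, covers 6 mg/dL (0.8%), depends on a site applying the parenthetical value, and is unlikely to arise at typical FCS levels. The Month 3 response classification and the planned summaries of change in TG are computed as written whichever figure stands in criterion 4. This is a minor correction. The arithmetic is firm; whether any patient would be affected cannot be told from the documents.

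**What to change.** Replace 8.4 with 8.47 mmol/L in Section 5.1, criterion 4, and in the synopsis. Two decimals are preferable, since 8.5 would overshoot 750 mg/dL by about 3 mg/dL. Alternatively, keep one decimal and add a sentence saying that the mg/dL value governs. If a mmol/L value is ever added to the response limit in Section 10.6.3, use the same conversion there.

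The cost is one figure in two places, or one sentence, at the next amendment. The 750 mg/dL limit, the retest rule and the response definition stay as they are.
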